### **1.2.2 Best Supportive Care (BSC)**

Best supportive care for MDS includes red blood cell transfusion, platelet transfusion and iron chelation therapy. Initiation of transfusion therapy should be based on clinical evaluation of anemia-related symptoms and co-morbid illness rather than on a defined hemoglobin level, especially because optimal hemoglobin levels are difficult to define for the elderly population. In clinical practice, pre-transfusion hemoglobin levels in MDS are generally maintained between 8 and 10 g/dL.

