#### 3.3.2 Inclusion criteria

1. Documented diagnosis of MDS according to World Health Organization (WHO) criteria that meets International Prognostic Scoring System (IPSS) classification of low or intermediate-1 risk disease at screening as determined by microscopic and standard cytogenetic analyses of the bone marrow and peripheral complete blood count (CBC).
  - Phase I dose escalation: patients who experienced ESA treatment failure or do not qualify (serum erythropoietin level > 500 U) for ESA treatment, and are refractory to or not amenable or eligible for established MDS therapy (HMA, lenalidomide)

Proprietary confidential information.

- Phase I expansion:
    - *Expansion cohort 1* (“pre-treated”): patients who experienced ESA treatment failure or do not qualify (serum erythropoietin level > 500 U) for ESA treatment and are refractory to established MDS therapy (HMA and /or lenalidomide)
    - *Expansion cohort 2* (“untreated”): patients who experienced ESA treatment failure or do not qualify (serum erythropoietin level > 500 U) for ESA treatment and who have not received prior HMA and/or lenalidomide (because not amenable or eligible for these treatments)
  - Phase II: patients who experienced ESA treatment failure or do not qualify (serum erythropoietin level > 500 U) for ESA treatment. For definition of further details of the phase II patients to be included the protocol will be amended based on Phase I results.
2. Patient has the evidence of symptomatic anemia according to the following criteria:
    - Phase I only: patients must have mean hemoglobin concentration < 10.0 g/dL of 2 measurements (not influenced by RBC transfusion within 7 days of measurement) and having received < 4 units of RBCs within 8 weeks prior to start of treatment OR,
    - Phase I/II: Patients must have received  $\geq 2$  units of RBCs for hemoglobin  $\leq 9.0$  g/dL within 8 weeks prior to start of treatment.
  3. Patient is non-responsive to, refractory to, or intolerant of ESAs, or ESAs are contraindicated or unavailable, or a documented serum erythropoietin level of > 500 U/L.
  4. Eastern Cooperative Oncology Group (ECOG) Performance Status  $\leq 2$  (refer to [Section 10.2](#)) (R14-0080).
  5. Age  $\geq 18$  years.
  6. Written informed consent which is consistent with International Conference on Harmonization – Good Clinical Practice (ICH-GCP) guidelines and local legislation.

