### Hematologic improvement (HI)

The HI will be evaluated in patients with abnormal pretreatment values defined as follows:

- Erythroid response (HI-E): Patients with a pretreatment hemoglobin  $<11$  g/dL demonstrate erythroid response if their hemoglobin increases by  $\geq 1.5$  g/dL for at least eight weeks, and there is a reduction in the units of red cell transfusions by an absolute number of at least four red cell transfusions per eight weeks compared with the pretreatment transfusion number in the previous eight weeks. Only red cell transfusions given for a hemoglobin  $\leq 9$  g/dL pretreatment will count in the red cell transfusion response evaluation.
- Platelet response (HI-P) — Patients with a pretreatment platelet count  $<100 \times 10^9/L$  demonstrate a platelet response if there is an absolute platelet increase of  $\geq 30 \times 10^9/L$  for patients starting with  $>20 \times 10^9/L$  platelets. For those with an increase from  $10 \times 10^9/L$  to  $>20 \times 10^9/L$  must have an increase of at least 100 percent.
- Neutrophil response (HI-N) — Patients with a pretreatment neutrophil count  $<1 \times 10^9/L$  demonstrate a neutrophil response if they have an at least 100 percent increase and an absolute increase  $>0.5 \times 10^9/L$ .
- Mean hemoglobin increase  $\geq 1.5$  g/dL — Time Frame: Up to approximately 48 weeks. Proportion of subjects achieving hemoglobin (Hgb) increase from baseline  $\geq 1.5$  g/dL over any consecutive 56-day period in absence of Red blood cell (RBC) transfusions.

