5.2.2 Secondary endpoints

The secondary endpoints in Phase I are

- RBC Transfusion Independence (RBC TI)
- Hematologic improvement neutrophils (HI-N)
- Hematologic improvement platelets (HI-P)
- Hematologic improvement erythroid (HI-E)
- Time to HI-E response
- Mean hemoglobin increase ≥ 1.5 g/dL
- Duration of Response (RBC Transfusion Independence, HI-N, HI-P, HI-E or Objective Response)
- Overall Objective Response (OR) [Complete Response (CR), Partial Response (PR), and Hematologic Improvement (HI)]

RBC Transfusion Independence (RBC-TI):

The definition of RBC TI is given in section 5.1.2.3 of the CTP. RBC-TI is evaluated in patients who are transfusion dependent at baseline. Percentages will be calculated using all treated patients, who are transfusion dependent at baseline, as the denominator.

The investigator's assessment as reported on the "Disease Assessment eCRF" will be used for the analysis of this endpoint. No derivation from the "Concomitant Blood Product Therapies eCRF" is planned. Consistency between these two eCRF pages will be reviewed during the trial's Medical Quality Review Meetings (MQRMs).

HI-N, HI-P and HI-E:

HI-N, HI-P and HI-E are defined in section 5.1.2.3 of the CTP. The investigator's assessment as reported on the "Disease Assessment eCRF" will be used for the analysis of these endpoints. No derivation from the "Laboratory eCRF" (or the "Concomitant Blood Product Therapies eCRF") is planned. Consistency between these eCRF pages will be reviewed during the trial's Medical Quality Review Meetings (MQRMs).

Time to HI-E response:

Time to HI-E response is defined only for patients who achieve a HI-E response as follows:

Time to HI-E response [days] = date of first assessment indicating HI-E response – date of first administration of trial medication + 1.

Mean hemoglobin increase ≥ 1.5 g/dL:

The definition of "Mean hemoglobin increase ≥ 1.5 g/dL" is given in CTP section 5.1.2.3.

Duration of Response:

Duration of objective response is defined only for patients who achieve an overall response of CR or mCR or RBC TI.

Duration of response is defined as:

Duration of Response [days] = date of outcome – date of first assessment indicating CR or mCR or RBC TI after first administration of trial medication + 1.

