6.7 BASELINE, TIME WINDOWS, AND CALCULATED VISITS

Study days and visits will be labelled according to the CTP's flow chart.

Unless otherwise specified, baseline is defined as the time-point closest to but prior to the first administration of trial medication in course 1. Note that for some trial procedures (for example body weight, vital signs, laboratory tests) this may be the value measured on the same day the trial medication was started. In these cases it will be assumed that the measurements were taken according to protocol, i.e. prior to first intake of any trial medication.

For laboratory values, baseline is defined as the latest time-point before the very first administration of any trial medication in course 1. When not only the examination date but also time are recorded, the examination time has to be taken into account when defining baseline. That is, a laboratory value on the same date as the first trial drug administration is considered as baseline value if and only if the time of laboratory value is before or the same as the time of first trial drug administration.

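### The hemoglobin-increase endpoint takes a single pre-dose value as baseline with no transfusion-free condition, so a transfusion shortly before Day 1 can hide a real increase

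*SAP*

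**What the plan says.** Protocol 5.1.2.3 defines the endpoint as "Proportion of subjects achieving hemoglobin (Hgb) increase from baseline" of at least 1.5 g/dL "over any consecutive 56-day period in absence of Red blood cell (RBC) transfusions". It does not say what baseline is. SAP 5.2.2 adds nothing, noting only that the definition "is given in CTP section 5.1.2.3". For RBC transfusion independence and for HI-N, HI-P and HI-E, the same SAP section names the investigator's assessment as the source. For the hemoglobin-increase endpoint it names no source.

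The baseline therefore comes from SAP 6.7. Its general rule reads "Unless otherwise specified, baseline is defined as the time-point closest to but prior to the first administration of trial medication in course 1", and its laboratory rule reads "For laboratory values, baseline is defined as the latest time-point before the very first administration of any trial medication in course 1". Neither asks for an average or for a minimum interval since a transfusion.

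The protocol does use a transfusion-aware hemoglobin measure elsewhere. The first route of inclusion criterion 2 (Protocol 3.3.2) takes the mean of two measurements, each "not influenced by RBC transfusion within 7 days of measurement".

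**The concern.** Hemoglobin in a transfused patient moves with the transfusion cycle, and a single value taken soon after red cells stands above the patient's own level. The protocol recognises this in one eligibility route, but the standard is not carried into the efficacy baseline. If the reference value is raised by donor blood, the change from baseline is understated and a real increase can fall short of 1.5 g/dL.

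SAP 7.5.2 tabulates the endpoint by dose cohort and in total. The dose-escalation cohorts are of three to six patients (Protocol 4.1.3), and Phase I has no control arm. A reader comparing cohorts could not tell a weak drug effect from an unlucky transfusion date.

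**Working it through.** No sample size or error rate in the plan depends on this baseline, so there is no stated figure to reproduce. Steps 1 to 3 compare the texts. Steps 4 to 7 are illustrations that rest on assumptions.

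1. **Which baseline applies.** Protocol 5.1.2.3 leaves baseline undefined, SAP 5.2.2 refers back to it, and SAP 6.7 applies unless something else is specified. Nothing else is.

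2. **What the transfusion-free condition covers.** In Protocol 5.1.2.3 it applies to the 56-day response period, not to the baseline.

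3. **Can a baseline follow closely on a transfusion?** Yes.
   - Criterion 2 has two routes joined by OR. The first allows fewer than 4 units in the previous 8 weeks. The second requires at least 2 units in 8 weeks, given for hemoglobin of 9.0 g/dL or less, and has no 7-day condition.
   - No exclusion criterion bars a transfusion just before Day 1.
   - Flow Chart 1, footnote 4, lets the sample be drawn up to 2 days before dosing, with no link to transfusion.
   - SAP 6.6 replaces a missing Visit 1 laboratory value by an earlier one, again with no transfusion condition.

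4. **Size of the shift.** The documents give no rise per unit. Assume 2 units at 0.5, 1.0 or 1.5 g/dL each, so S = 2 × rise = 1.0, 2.0 or 3.0 g/dL. Assume a linear decline to the pre-transfusion level over the interval T, so the part remaining at day t is S(1 − t/T). To be counted, a patient must rise above the pre-transfusion level by 1.5 + S(1 − t/T):

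| S (g/dL) | baseline just after transfusion | 7 days after, T = 28 (75% remains) | 7 days after, T = 14 (50% remains) |
|---|---|---|---|
| 1.0 | 2.5 | 2.25 | 2.0 |
| 2.0 | 3.5 | 3.0 | 2.5 |
| 3.0 | 4.5 | 3.75 | 3.0 |

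   The pre-transfusion level is the lowest possible reference. Measured from the cycle mean, the requirement with a baseline just after transfusion is 1.5 + S/2 = 2.0, 2.5 or 3.0 g/dL. If the baseline falls at a random point of the cycle, a true sustained rise of 2.0 g/dL over the cycle mean is counted with probability (2.0 − 1.5 + S/2)/S = 1.00, 0.75 or 0.67.

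5. **Can a trough baseline give false credit?** Suppose the baseline is at the trough, blood follows, and the 56-day window opens at once. With no drug effect, the mean rise over the window is S − 28S/T.
   - S = 2.0, T = 28: 2.0 − 2.0 = 0.
   - S = 2.0, T = 14: 2.0 − 4.0 = −2.0.
   - Reaching 1.5 needs T ≥ 28S/(S − 1.5). For S = 2.0 that is 56/0.5 = 112 days; for S = 3.0 it is 84/1.5 = 56 days. For S of 1.5 or less it cannot happen.

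   A patient transfused every 2 to 4 weeks is thus not credited unless the need for blood changes.

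6. **A constructed patient.** Own hemoglobin is 8.0 g/dL, within the 8 to 10 g/dL that Protocol 1.2.2 gives for pre-transfusion levels. Two units are given on the day before dosing, the pre-dose value is 9.8, and 56 transfusion-free days follow at 10.2. SAP 6.7 gives 10.2 − 9.8 = +0.4, a non-responder. Against 8.0 it is 10.2 − 8.0 = +2.2, a responder. The implied rise is 1.8/2 = 0.9 g/dL per unit, inside the assumed range.

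7. **Leverage.** One patient moves a cohort rate by 1/6 to 1/3 (17 to 33 points) and the overall rate by 1/27 (3.7 points; 21 + 6 patients in the protocol synopsis).

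**The case against.** The case on the other side is substantial.

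- **The eligibility standard.** A reader might infer that the protocol accepts hemoglobin at entry only as a transfusion-free mean, and that the endpoint then drops that protection. The documents do not support this. The standard belongs to one of two alternative routes, and the endpoint never contained it.
- **Direction.** A reader might infer that errors run equally both ways, with trough baselines inflating response. Step 5 shows that the 56-day condition largely prevents this. A trough baseline does lower the bar relative to the cycle mean. But the patient must then hold that level for 56 days without blood, and the repair proposed here would itself tend to pick values nearer the trough.
- **Size.** A reader might infer that the baseline error equals the response threshold. That rests wholly on the assumed rise per unit. With 1 unit at 0.5 g/dL the initial shift is only 0.5.
- **The patient is not lost.** Someone transfused within 56 days before Day 1 is transfusion dependent under Protocol 5.1.2.3. If that patient then goes 56 days without red cells, the RBC transfusion independence criterion is met, and that endpoint is in the same frequency table. This stands, and it limits the harm.
- **Low stakes.** This is one of eight secondary endpoints, summarised descriptively. The MTD does not use it, and the Phase II analyses are cancelled (SAP 4.2). This also stands.

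None of this supplies a transfusion-aware baseline for the endpoint.

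**Conclusion.** The gap is real and narrow. By default the endpoint is measured from a single pre-dose hemoglobin value that may be raised by a recent transfusion, and the main consequence is missed responders. Under the assumed 2 units and 0.5 to 1.5 g/dL per unit, the initial shift is 1 to 3 g/dL, fading with time since transfusion. The true size is unknown, because the documents give neither the rise per unit nor how many of the 27 patients were transfused shortly before baseline. Patients without a recent transfusion are unaffected. This is a worthwhile, inexpensive clarification of a secondary descriptive endpoint. It does not show that reported response rates would be inflated, and it has no bearing on the MTD.

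**What to change.** In SAP 5.2.2 and 6.7, for the hemoglobin-increase endpoint only:

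- Define baseline as the mean of the last two pre-treatment hemoglobin values not influenced by an RBC transfusion within 7 days, or the one such value if only one exists.
- If none exists, use the SAP 6.7 value, flag the patient, and keep the patient in the denominator, in line with the all-patients default in SAP 7.
- List days since the last RBC transfusion beside each baseline, and show the frequency table under both baselines.
- Leave the safety laboratory baseline unchanged. A special baseline has a precedent: the tumor lysis analysis in SAP 7.8.1.2 uses its own.

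The cost is SAP wording and a merge of laboratory and transfusion dates. Hemoglobin is scheduled at screening and Day 1, transfusions are recorded back to 3 months before treatment (Protocol 6.2.1), and SAP 5.2.2 mentions a blood-product eCRF page. It should be confirmed that this page holds dates for the week before each pre-treatment sample.

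Some patients will have one qualifying value or none. With regular transfusion, a randomly timed sample falls within 7 days of one in 7/28 = 25% of cases at a 28-day interval and 7/14 = 50% at a 14-day interval, so the fallback is needed. The 7-day rule also leaves some effect: on the linear model, 75% of the shift remains at day 7 of a 28-day cycle and 50% at day 7 of a 14-day cycle. That is why the listing and the two-baseline table belong with it.

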**FU:** Follow-up starts 4 weeks after the EOT visit; Phase I patients: visits or telephone calls will occur at least every 4 weeks for 6 months. After the 6th follow-up visit, the patient will be considered off trial. Phase II patients: visits or telephone calls will occur at least every 4 weeks until 12 months after the last administration of BI 836858, after which these visits will occur every 6 months until the end of the trial. After implementation of CTP version 5.0, no further follow-up visits after EoR, unless follow-up is for S(AE) that occurred before EoR period.

\* The planned duration of a treatment cycle is 28 days; there will be two administrations of BI 836858 per cycle, on Days 1 and 15. All assessments should be performed prior to dose administration on dosing days, unless otherwise specified.

\*\* These visits are only for those patients who have received BI 836858 that are non-PD and equivocal as to if clinical benefit has been established, per investigator judgment, after 4 Cycles; up to 2 additional introduction cycles allowed prior to end of introduction treatment.

- 1 Visit window of +1 day only allowed beginning in Cycle 3 and for all subsequent cycles. In Cycles 1 and 2 visit window not allowed
- 2 Review of inclusion/exclusion criteria during screening and again on day of first administration.
- 3 After informed consent and review of inclusion/exclusion criteria (timing described in footnote 2). For phase II, randomization should be performed as close to the first treatment dose as possible. It may be performed on the day of the first administration (Cycle 1 day 1) prior to patient treatment, but no later than 21 days after patient signs informed consent.
- 4 For details refer to [Section 5.2.3.1](#). Urine has to be measured only at screening, EOC4 and EOT. Safety laboratory assessments may be completed up to 2 days prior to administration, or BSC treatment on trial (Phase II). An additional safety lab will be collected on day 2 (i.e., 24 hours after the first administration of BI 836858) and 24 hours after the first higher dose for patients who participate in intra-patient dose escalation. Other lab tests to be included: haptoglobin, direct Coombs test, and bilirubin (direct and indirect).

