#### 4.1.4 Drug assignment and administration of doses for each patient

Prior to inclusion of a new patient during the cohort dose escalation phase, the Investigator has to confirm the actual dose tier of BI 836858 for the patient with the Sponsor who oversees the cohort dose escalation steps and the safety data of patients from all trial sites. BI 836858 will be administered as an intravenous infusion every 14 days under the supervision of the Investigator or designated personnel.

BI 836858 may be administered at any time during the day.

it is recommended to

start the infusion during the morning hours.

Premedication to prevent infusion-related reactions is obligatory 30 minutes (up to 120 min before start of administration of BI 836858 is permissible) prior to the first and second administration of BI 836858, unless a contraindication for premedication exists, and should include:

- Acetaminophen/Paracetamol 650 mg - 1000 mg p.o., or equivalent
- Antihistamine p.o. or i.v., equivalent to Diphenhydramine 50 mg i.v.
- Glucocorticoid i.v., equivalent to prednisolone 100 mg

If BI 836858 has been well tolerated without signs of infusion-related reactions in the first administration, glucocorticoid premedication may be reduced to a dose equivalent to 50 mg prednisolone for the second through fourth administrations, and in case this is well tolerated reduce the glucocorticoid with the 5th infusion (25 mg with the 5th and 0 mg with the 6th infusion.) However, in case an administration of BI 836858 was not well tolerated the premedication with prednisolone can be re-escalated up to 100 mg.

Before the administration of BI 836858, adverse events and safety laboratory will be assessed. To start or continue treatment with further administrations, all of the following criteria must be met:

- (1) Neutrophils  $\geq 1000 /\mu\text{L}$  ( $1.0 \times 10^9/\text{L}$ )
- (2) Platelets  $\geq 50,000 /\mu\text{L}$  ( $50 \times 10^9/\text{L}$ ), unless CTCAE Grade 3 or 4 thrombocytopenia was preexistent prior to trial entry. Patients who go from Grade 3 to Grade 4 thrombocytopenia after treatment may continue on study provided that post-transfusion platelet count is at least 20,000/uL before therapy is given.
- (3) Acceptable tolerability (in case of an AE at the planned start of a further administration, patients may continue therapy only after recovery to a level which would allow further therapy, i.e. CTCAE grade 1 or baseline value.)

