5.1 PRIMARY ENDPOINTS

The primary endpoints in the Phase I part of the trial are the MTD and the number of patients with dose limiting toxicities (DLTs) during the MTD evaluation period.

Maximum tolerated dose (MTD) and number of patients with DLTs during the MTD evaluation period:

The MTD is defined as the highest dose of BI 836858 with less than 25% risk of the true DLT rate being above 33% during the MTD evaluation period. The other primary endpoint, the number of patients with DLTs during the MTD evaluation period will be used to determine the MTD.

MTD evaluation period:

The MTD evaluation period is defined as the time from the first administration of trial medication to start of the third administration of BI 836858, excluding the day of the third administration of BI 836858. In case the third infusion of BI 836858 is not administered, the evaluation period ends 30 days after the last administration.

In case a patient has not completed the required number of administrations due to BI 836858 related toxicity, he/she will not be replaced and this will be considered as DLT. However, patients who have not completed the required number of administrations of BI 836858 for reasons other than BI 836858 related toxicity will be replaced. Patients who were replaced during the MTD evaluation period will not be considered for MTD evaluation. That is, a patient will be considered evaluable for MTD assessment if he/she received at least 2 administrations of BI 836858 or if he/she received less than 2 administrations due to DLT.

The MTD estimate after the dose escalation part of the trial will be obtained on the basis of DLTs observed during the MTD evaluation period. However, for those patients who receive more than one cycle of the treatment, all AEs that constitute a DLT will be considered in the final determination of the dose recommended for the Phase II part.

As part of this additional analysis the probabilities of the Bayesian 2-parameter logistic regression model with overdose control will be also computed including all considered DLTs.

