6. GENERAL ANALYSIS DEFINITIONS

6.1 TREATMENTS

In the Phase I part, treatments are not randomized (open-label, dose escalation). Different dose levels (planned and intermediate) of the investigational medicinal product will be evaluated. The data will be presented for all dose cohorts separately, in particular, patients will be analysed by the treatment group initially assigned in the first treatment course. In addition, totals over all dose cohorts will be given.

“Analysing treatment periods” will be used for reporting of treatment emergent adverse events (AE) and to differentiate between screening, on-treatment, post-treatment and post-study safety data. The inequalities start date \leq onset date of AE $<$ stop date will determine whether the AE will be assigned to the “analysing treatment period” or not. Table 6.1:1 defines the “analysing treatment periods” which will be used for reporting of treatment emergent AEs and safety laboratory parameters.

Table 6.1:1 Definition of analysing treatment periods

| Analysing treatment period | Start date (including) | Stop date (excluding) |
|----------------------------|---|---|
| Screening | Date of informed consent | Date of first administration of trial medication |
| MTD evaluation period | Date of first administration of trial medication | Date of third infusion or (if the third infusion was not administered) Date of first administration of trial medication + 28 days |
| On-treatment | Date of first administration of trial medication | Start date of ‘Follow-up’ |
| Follow-up | Date of end of REP +1 day, i.e. Date of last administration of trial medication + 30 days of REP + 1 day | Start date of ‘Post-study’ |
| Post-study | Last date patient status obtained / last date patient known to be alive + 1 (if patient is lost to follow-up) / date of refusal + 1 day / the date patient died + 1 | DBL + 1 day |

Data recorded between the first administration of trial medication until up to 30 days (Residual effect period; REP) after the last administration of trial medication will be considered as on-treatment.

In addition, to justify the MTD determination, AEs occurring during the MTD evaluation period will be presented separately from those occurring during the complete on-treatment period.

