7.8.1.2 Adverse events

Unless otherwise specified, the analyses of adverse events (AEs) will be descriptive in nature. All analyses of AEs will be based on the number of patients with AEs and NOT the number of AEs. The analyses will be based on BI standards. Adverse events will be coded with the most recent version of MedDRA. The severity of AEs will be scaled according to CTCAE version 4.0.

For analysis of AE attributes such as duration, severity, etc. multiple AE occurrence data on the CRF, will be collapsed into AE episodes provided that all of the following applies:

- The same MedDRA lowest level term was reported for the occurrences.
- The occurrences were time-overlapping or time-adjacent (time-adjacency of 2 occurrences is given if the second occurrence started on the same day or on the day after the end of the first occurrence).
- Treatment did not change between the onset of the occurrences OR treatment changed between the onset of the occurrences, but no deterioration was observed for the later occurrence.

For each patient, all episodes with the same preferred term (PT) (system organ class, SOC) will be condensed to one AE record using a worst case approach for all AE attributes including CTCAE grading.

The analysis of adverse events will be based on the concept of treatment emergent adverse events, where a treatment emergent AE has an onset in the analyzing treatment period. All adverse events occurring before first intake of trial medication will be assigned to 'screening' and all adverse events occurring after last intake of trial medication + 30 days will be assigned to 'post-treatment' (in randomized trials for listings only). For details on the treatment definition, see [Section 6.1](#). In addition, a listing will be provided, detailing the actual treatment on the day when the adverse event started. For screening and post-study period, AEs will be listed.

An overall summary of adverse events will be presented. This will include the number of patients with AEs by the highest CTCAE grade. The frequency of patients with adverse events will be summarized by treatment, highest CTCAE grade, primary system organ class and preferred term (PT). Separate tables will be provided for the followings:

- serious adverse events (SAEs),
- drug-related SAEs,
- drug-related AEs,
- AEs leading to permanent discontinuation of trial medication,
- AEs leading to death,
- DLTs, and

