7.8.2 Laboratory data

The analyses of laboratory data will be descriptive in nature and will be based on BI standards (8). The same on-treatment period as considered for the analysis of AEs will be applied for laboratory values. Patients having at least one post-baseline laboratory value will be displayed in the descriptive analyses.

Safety laboratory examinations include hematology, biochemistry, coagulation and qualitative urine analysis:

| | |
|--------------|--|
| Hematology | Hemoglobin, red blood cell count (RBC), white blood cell count (WBC) with differential (neutrophils, basophils lymphocytes, monocytes, eosinophil, reticulocytes), platelets (PLT) |
| Biochemistry | Glucose (plasma), sodium, potassium, calcium, inorganic phosphate, creatinine, AST, ALT, alkaline phosphatase (AP), lactate dehydrogenase (LDH), bilirubin (total and direct), urea (preferred) or BUN, total protein, albumin, uric acid, IgG, IgM, IgA and direct antiglobulin (direct Coombs), Free haemoglobin(serum), Haptoglobin |
| Coagulation | Activated partial thromboplastin time (aPTT), prothrombin time (PT), international normalised ratio (INR) where indicated (e.g. treatment with vitamin K antagonists) |
| Urine | pH, glucose, erythrocytes, leukocytes, protein, nitrite |

Neutrophil and platelet counts of each patients will be plotted in log scale graphs.

Descriptive statistics, including change from baseline and frequency of patients with transitions relative to the reference range, will be provided. CTCAE grades for applicable laboratory parameters will be calculated according to CTCAE version 4.0. The following outputs will be presented:

- Worst CTCAE grade experienced during the on-treatment phase.
- Transitions of CTCAE grade from baseline to worst laboratory value, from worst to last laboratory value during the on-treatment phase, and from baseline to last laboratory value.

Worse laboratory value and its CTCAE grade (highest CTCAE grade) over all courses will be calculated for each laboratory parameter.

The last laboratory value on treatment is the laboratory value of the last visit during the on treatment period of each patient.

Patients with missing CTCAE grade at baseline or no baseline value but with post-baseline values will be displayed in the category “Missing CTCAE grade at baseline” for those laboratory parameters where CTCAE grading is applicable.

Possible clinically significant abnormal laboratory values:

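### By the dates in SAP Table 6.1:1, a Day 1 pre-dose laboratory value is both baseline and on-treatment, and the start of the DLT window is stated in two ways

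*SAP*

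**What the plan says.** Table 6.1:1 in SAP 6.1 defines the analysis periods by start date (included) and stop date (excluded). Its on-treatment row begins "On-treatment | Date of first administration of trial medication". The MTD evaluation period starts on the same date, and screening stops on that date, excluded. The AE assignment rule above the table compares dates only. The table is one "which will be used for reporting of treatment emergent AEs and safety laboratory parameters".

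SAP 7.8.2 carries this over: "The same on-treatment period as considered for the analysis of AEs will be applied for laboratory values". It then asks for the worst CTCAE grade on treatment and for transitions from baseline to worst, worst to last and baseline to last.

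SAP 6.7 sets the laboratory baseline by clock time: "a laboratory value on the same date as the first trial drug administration is considered as baseline value if and only if the time" of the sample is at or before that of the first dose. In Protocol Flow Chart 1, assessments on dosing days precede the dose unless otherwise specified, and footnote 4 adds: "Safety laboratory assessments may be completed up to 2 days prior to administration".

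Other text starts from the administration, not the date. SAP 5.1 defines the MTD evaluation period as "the time from the first administration of trial medication to start of the third administration of BI 836858". SAP 7.8.1.2 says: "All adverse events occurring before first intake of trial medication will be assigned to" screening. The narrative below Table 6.1:1 and Protocol 7.3.3 also count from the first administration.

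**The concern.** A value cannot serve both as the reference and as part of what is compared with it. If the pre-dose Day 1 value is in the on-treatment set, the baseline-to-worst table cannot show improvement for that patient, and the worst-to-last table can report recovery from a low point that came before any drug. Because the sample may be drawn up to two days earlier, two patients with the same course can be tabulated differently for a scheduling reason. Haematology is where this matters most: Phase I patients enter with symptomatic anaemia (Protocol 3.3.2), and haematologic events are the main anticipated toxicity (Protocol 2.3).

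The AE side is a conflict between rules. The table and the text give different answers for an event on Day 1 before the infusion, and that boundary opens the window for the primary DLT endpoint.

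**Working it through.** **Step 1. Apply the rules to a test case.** Assume a first infusion on Day 1 at 10:00, with a laboratory sample and an AE onset both at 08:00.

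| Record at 08:00 | By Table 6.1:1 dates | By the text |
|---|---|---|
| Laboratory value | On-treatment (via 7.8.2) | Baseline (6.7); before on-treatment (6.1 narrative) |
| AE | On-treatment and in the MTD evaluation period; not screening | Screening (7.8.1.2); outside the MTD evaluation period (5.1) |

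For the laboratory value, the post-baseline sentence in SAP 7.8.2 decides only which patients are displayed. It does not remove the baseline value from the worst or last value.

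**Step 2. Effect on the laboratory tables.** Take a hypothetical patient with Grade 3 before dosing and Grade 2 at every later visit.
- Sampled on Day 1: worst on-treatment grade 3; baseline to worst 3→3; worst to last 3→2.
- Sampled on the day before: worst on-treatment grade 2; baseline to worst 3→2; worst to last 2→2.

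The possible clinically significant count (SAP 7.8.2) needs a rise of at least one grade over baseline, so a baseline value cannot trigger it.

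**Step 3. How often could it matter?** If a patient's raw values are exchangeable over time, with k post-dose samples and no ties, baseline is the worst with probability 1/(k+1). The scheduled samples come from Flow Chart 1, its footnote 4 and Protocol 6.2.2.2:
- Cycle 1: Days 2, 8, 15, 22 = 4
- Cycle 2: Days 1, 8, 15, 22 = 4
- Cycle 3: Days 1, 15 = 2
- Cycle 4: Days 1, 15 = 2
- End of Cycle 4 = 1

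Cycle 1 only: k = 4, so 1/5 = 20%. If the end-of-treatment sample falls on day 30 after the last dose it also counts, giving 1/6 = 17%. Through the end of Cycle 4: k = 4+4+2+2+1 = 13, so 1/14 = 7%.

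The tables show grades, and a later value of the same grade leaves the worst grade unchanged. Under exchangeability these figures are therefore upper bounds on the share of patients affected. Without it, the share could be higher in patients whose counts improve.

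**Step 4. What one misassigned event could do to the dose model.** I fitted the model and prior of Protocol 7.1 on a numerical grid. It comes close to the protocol's own figures: prior overdose probability at 320 mg 0.443 (Table 7.1: 2 gives 0.441), and scenario 9 about 0.70 (Table 10.3: 1 gives 0.709). With 0/3 DLTs at each of 20, 40, 80 and 160 mg (hypothetical), the overdose probability at 320 mg is:

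| DLTs / patients at 320 mg | P(overdose) |
|---|---|
| 0/3 | 0.030 |
| 1/3 | 0.264 |
| 1/4 | 0.176 |
| 1/6 | 0.080 |

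The 0.25 limit is crossed only in the three-patient case.

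**The case against.** The strongest reply concerns AEs. A reader might infer from the table that a Grade 3 or higher reaction to premedication before the infusion would count as a DLT. Protocol 4.1.4 makes the gap real ("Premedication to prevent infusion-related reactions is obligatory 30 minutes" ahead, up to 120 minutes allowed), and the first DLT criterion in Protocol 5.2.1.1 asks only that the event not be disease-related. But SAP 5.1, SAP 7.8.1.2, the SAP 6.1 narrative and Protocol 7.3.3 all exclude such an event. It would count only if a programmer let the table override them. The documents report no such event, and the Data Safety Board took escalation decisions after each cohort with individual patient profiles in hand (Protocol 3.1.1.1), before the SAP was final. Protocol 5.2.2.2 also lists an onset date but no onset time for AEs in general, so treating untimed Day 1 events as on-treatment is the cautious default. This part of the reply stands: what remains is an inconsistency in wording.

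On laboratory data, it can be said that the date inequality is written for AEs, that 7.8.2 speaks of post-baseline values, and that it relies on an internal laboratory standard (SAP reference 8) that may already select post-baseline values. That standard is not available here, so this cannot be ruled out. It does not settle the matter, because the SAP states that the table covers laboratory parameters and no sentence in it excludes the baseline value. SAP 6.7 itself is sound; the fault lies in Table 6.1:1 and its use in 7.8.2.

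**Conclusion.** The laboratory overlap holds as the SAP is written, for patients whose baseline sample is drawn on Day 1 before dosing. It affects the worst-grade output and the two transitions that involve the worst value. It does not affect patients sampled earlier or the possible clinically significant count. The 20% and 7% should not be read as shares of patients misreported: they are upper bounds under exchangeability.

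The start of the primary DLT window is stated in two ways and should be stated once. The stronger inference, that the MTD result is at risk, is not supported. It needs an unlikely event in a short interval, the table taking precedence over explicit text, and a top-dose cohort as small as three. With four patients the overdose probability is 0.176 and with six it is 0.080, both under the limit. These values assume three patients without a DLT at each lower dose; the documents do not give the actual numbers per dose.

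Priority: minor. The laboratory tables concerned are descriptive.

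**What to change.** 1. In SAP 7.8.2, state that worst, last and transition laboratory summaries use only values after the baseline value defined in SAP 6.7.
2. In Table 6.1:1, start both the on-treatment period and the MTD evaluation period at the first administration, and end screening there, to agree with SAP 5.1 and 7.8.1.2.
3. Add a tie-break for Day 1 AEs: those known to precede the infusion go to screening; those of unknown order stay on-treatment.

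The cost is a few lines of SAP wording and a small programming change. SAP 6.7 already uses laboratory sampling times where recorded, and Protocol 4.1 requires infusion start times in the eCRF. Untimed Day 1 AEs would be classified as they are now by the table.
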